OS	Overall survival
PCS	Potentially clinically significant
PD	Progressive disease
PFS	Progression-free survival
PK	Pharmacokinetic
PR	Partial response
R/R	Relapsed/refractory
Rel Day	Relative study day
RFS	Relapse-free survival
SAE	Serious adverse event
SAP	Statistical analysis plan
SCT	Stem cell transplant
SD	Standard deviation
SI	International System of Units
SOC	System organ class
TEAE	Treatment-emergent adverse event
TTCR	Time to complete response (CR + CRc)
TPP	Time to progression
TTR	Time to response (CR + CRi + CRc + PR)
ULN	Upper limit of normal
US	United States
VOD	Veno-occlusive disease
WHO	World Health Organization

1. INFORMATION FROM THE STUDY PROTOCOL

1.1. Introduction and Objectives

The overall purpose of study STML-401-0114 is to support the development of SL-401 (ELZONRIS® [Tagraxofusp-erzs]; “tagraxofusp”) and assess safety and clinical efficacy of the product in treatment of patients with first-line blastic plasmacytoid dendritic cell neoplasm (BPDCN), relapsed/refractory (R/R) BPDCN, R/R acute myeloid leukemia (AML), and firstline high risk AML. The primary focus of this document is the assessment of efficacy and safety of tagraxofusp in first-line BPDCN patients with supporting evidence from the remaining populations. Additional analyses will be performed on the R/R BPDCN, R/R AML, and firstline high risk AML patients.

AML is characterized by the uncontrolled proliferation of immature myeloid cells in the bone marrow (BM) and peripheral blood, resulting in the development of anemia, neutropenia, and thrombocytopenia, and associated complications such as serious infections. The median age at diagnosis is 67 years, and 5-year survival across all ages, treatments, and other prognostic groups is 24% ([National Cancer Institute 2013](#)).

BPDCN is an uncommon hematological malignancy that is characterized by the clonal proliferation of malignant plasmacytoid dendritic cells ([Facchetti, et al. 2003](#)). While the disease expression of BPDCN is similar to AML, BPDCN was characterized as a distinct cancer type as early as 1994 ([Adachi, et al. 1994](#)) though little was known of the disease biomarkers until the mid-2000s.

BPDCN most commonly affects middle-aged and older patients and is approximately 3.5-fold more common in men than women. The median age at diagnosis is 66 years and is lower for women than men. The true incidence and prevalence of BPDCN is not precisely known. However, based on a published report ([Wang, et al. 2012](#)), BPDCN constitutes approximately 0.44% of the incident cases of hematologic cancers annually, or approximately 700 and 1,000 incident cases annually in the United States (US) and Europe, respectively, based on published data of hematologic cancer cases.

The clinical features and evolution of BPDCN consist primarily of 2 patterns ([Assaf, et al. 2007](#); [Brody, et al. 1995](#); [Herling and Jones 2007](#); [Petrella, et al. 2005](#); [Petrella, et al. 1999](#); [Reichard, et al. 2005](#); [Suzuki, et al. 2005](#)). The first pattern (90% of cases) is characterized by an indolent onset dominated by cutaneous lesions followed by tumor dissemination. The second pattern shows features of an acute leukemia with systemic involvement from the outset, and multiple skin nodules are frequently present ([Suzuki, et al. 2005](#)). BPDCN most typically presents with skin lesions as well as extracutaneous malignant disease in the BM, blood, lymph nodes, spleen, and other organs. Despite the frequent appearance of a somewhat indolent clinical presentation at the outset, the course of BPDCN is highly aggressive and the median survival is approximately 12-14 months ([Bekkenk, et al. 2004](#); [Feuillard, et al. 2002](#); [Herling and Jones 2007](#); [Jacob, et al. 2003](#); [Petrella, et al. 2005](#)). The disease almost always results in a terminal leukemic phase with proliferation of BPDCN blasts in the BM and peripheral blood, leading to decreased blood cell counts with resultant infections, bleeding, and invariably death.

Diphtheria toxin (DT) Interleukin-3 (IL-3) fusion protein (tagraxofusp) is a novel biologic targeted therapy directed to the IL-3 receptor (IL-3R), a biomarker that is over-expressed on AML and BPDCN blasts and cancer stem cells (CSCs) relative to normal hematopoietic stem

cells (Jordan, et al. 2006; Jordan, et al. 2000; Tehranchi, et al. 2010). Tagraxofusp is comprised of recombinant human IL-3 genetically fused to a truncated DT, in which the native receptorbinding domain of DT has been replaced with IL-3. The IL-3 domain of tagraxofusp is able to target the agent to cells that over-express IL-3R, leading to receptor-mediated endocytosis and localization of tagraxofusp to early endosomes. This allows tagraxofusp to kill cells in a distinct manner from other cancer therapeutics. First, tagraxofusp is a targeted therapy directed to the IL-3R that is differentially present on tumor bulk and/or CSCs versus normal hematopoietic stem cells. Second, tagraxofusp utilizes a payload that is not cell cycle-dependent. Therefore, it is designed to kill not just highly proliferative tumor bulk, but also relatively quiescent CSCs. Tagraxofusp utilizes a payload that may not be subject to multi-drug resistance mechanisms typically used by CSCs to evade traditional therapies. The payload also kills cells in a manner that is distinct from that of other available therapies, which is another reason why tagraxofusp is an effective addition to the therapeutic armamentarium against certain hematologic malignancies.

Tagraxofusp in frozen liquid formulation was approved by the US Food and Drug Administration (FDA) in 2019 for treatment of BPDCN in adults and pediatric patients 2 years and older based primarily on the efficacy findings from this study, STML-401-0114. STML401-0114 was designed as a Phase 1/2 dose escalation and expansion study targeting patients with BPDCN or AML. Stage 1 (dose escalation) enrolled patients with BPDCN, R/R AML, and previously untreated AML considered high risk for progression and/or unfit for standard therapy. Stage 2 (expansion) enrolled additional patients with first-line BPDCN, patients with R/R BPDCN, and R/R and untreated high risk AML patients. Stage 3 was a confirmatory cohort to test pre-specified hypotheses regarding the efficacy of tagraxofusp among first-line BPDCN patients in preparation for the biological licensing application (BLA) filing. Stage 4 initiated enrollment after August 29, 2016 through January 7, 2019 and included R/R BPDCN patients and first-line BPDCN patients enrolled after March 17, 2017. Patients enrolled into Stage 4 were treated with lyophilized formulation of tagraxofusp. At the time of BLA filing and approval limited data were available from Stage 4.

The purpose of this document is to support an updated report on the clinical efficacy and safety of tagraxofusp, emphasizing both the Stage 4 results that were not previously reported and the overall conclusions from the duration of the trial. Emphasis is on the results from BPDCN patients. Updated data are included in this report from an additional 44 patients enrolled into Stage 4 (42 treated) after the data cut-off for the original clinical study report dated May 09, 2018.

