12.3 Determination of Sample Size

The sample size was originally planned to be approximately 40-50 patients with BPDCN, including approximately 40 first-line patients planned to be treated with the optimal SL-401 dose as determined in the completed Stage 1 of this study (12 µg/kg/day). In addition, up to approximately 36 patients with R/R AML were planned to be enrolled in Stage 2 of the study.

In Stage 3, a sufficient number of patients were enrolled to ensure 10 evaluable patients were included, with evaluable patients being those with a diagnosis of BPDCN, as confirmed via

central pathology review who received at least 1 dose of SL-401. The sample size allocated for Stage 3 is intended to satisfy specific statistical criteria established by the Sponsor at the request of the US FDA.

[REDACTED]

[REDACTED] The primary efficacy analysis for Stage 3 compares the lower bound of a two-sided 95% Clopper Exact confidence interval surrounding the observed CR rate to a clinically meaningless value of 10%. Statistical significance is determined if the lower bound of this confidence interval falls above the rate of 10%. Assuming a CR rate of at least 60%, a sample size of a minimum of 10 first-line BPDCN patients provides at least 90% power for this the primary efficacy assessment.

[REDACTED]

To avoid possible selection bias, all first-line BPDCN patients enrolled in this time period are included in the Stage 3 analysis. This sample size also ensures there are 10 patients in the PP analysis population.

After the maximum number of patients with first-line BPDCN in Stage 3 were enrolled, subsequent first-line BPDCN patients are enrolled in Stage 4. Furthermore, any patient with R/R BPDCN enrolled in this study on or after 26 October, 2016, will be allocated to Stage 4. Enrollment will continue in Stage 4 up until enrollment of up to approximately 145 patients or prior termination of the study.

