1.2. Study Design

1.2.1. Synopsis of Study Design

This study is a non-randomized, open-label, multicenter study divided into 4 stages: dose escalation (Stage 1), expansion (Stage 2), pivotal (Stage 3), and supportive efficacy and safety (Stage 4). The targeted patient populations are patients with:

- First-line BPDCN for primary efficacy and safety profile of tagraxofusp (Stages 1 to 4).
- R/R BPDCN for supportive efficacy and supportive safety profile of tagraxofusp (Stages 1, 2 and 4).
- R/R AML and high-risk first-line AML for supportive efficacy and supportive safety profile of tagraxofusp (Stages 1 and 2).

A cycle of therapy consists of administration of tagraxofusp at the identified dose for 5 consecutive days every 21 days (with the entire cycle duration lasting 21 days). tagraxofusp is supplied as tagraxofusp Injection frozen solution (1 mg/mL) for Stages 1, 2, and 3. A lyophilized formulation of tagraxofusp (for Injection, lyophilized powder, for solution; 1 mg/mL) was supplied for dosing in selected patients with AML in Stage 2 and for BPDCN patients enrolled in Stage 4 after 17 March 2017.

Stage 4 is planned to continue enrollment of first-line and R/R BPDCN patients to further characterize the efficacy and safety of tagraxofusp and to evaluate the lyophilized formulation in a subset of patients. Pooled analysis of Stage 4 data with other stages will be performed at the time of the primary analysis of study results.

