3. GENERAL STATISTICAL METHODS

3.1. Sample Size Justification

The sample size was originally planned to be approximately 40-50 patients with BPDCN, including approximately 40 previously untreated patients planned to be treated with the tagraxofusp dose as determined in the completed Stage 1 of this study (12 µg/kg/day). In addition, up to approximately 36 patients with R/R AML were planned to be enrolled in Stage 2 of the study. These sample sizes were not based on a formal statistical approach but were considered reasonable to accomplish study objectives for these phases of the trial.

In Stage 3, a sufficient number of patients were enrolled to ensure 10 evaluable patients would be included, with evaluable patients in the mITT population, defined as patients with a diagnosis

of BPDCN, as confirmed via central pathology review, and who received at least 1 dose of tagraxofusp. [REDACTED]

[REDACTED] The primary efficacy analysis for Stage 3 compared the lower bound of a 2-sided 95% Clopper Exact confidence interval (CI) on the observed CR rate to a clinically meaningless value of 10%. Assuming a CR rate of at least 60%, a minimal sample size of 10 first-line BPDCN patients provided at least 90% power for the primary efficacy assessment. Due to the criteria for evaluability in the BPDCN mITT population requiring central pathology review, 13 first-line BPDCN patients were enrolled in Stage 3 between October 26, 2016 and March 17, 2017. Statistical significance was determined when the lower bound of this CI fell above the rate of 10%.

After completion of enrollment of patients with first-line BPDCN in Stage 3, 39 first-line BPDCN patients were enrolled in Stage 4 (37 treated with study drug and 2 screen failures) and 5 R/R BPDCN enrolled in this study after 29 August, 2016 were enrolled in Stage 4.

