4.5. Summary of Immunogenicity Parameters

Immunogenicity parameters will be summarized for FL BPDCN, R/R BPDCN, all BPDCN, Stage 4 (lyophilized formulation) only, and all patients pooled across all doses and stages.

Analyses will be conducted in accordance with the principles outlined in ([Shankar, et al. 2014](#)) and will include:

- Incidence of patients with positive anti-drug antibodies, specific anti-hIL-3 antibodies, and neutralizing antibodies will be assessed by cycle uniquely through cycle 6 and cycles >6 , collectively. Incidence will be summarized by number and percent of patients with positive antibody results.
- Mean fold increase from baseline and geometric mean titer are tabulated by scheduled assessments. Summary statistics will include mean, SD, median, min, and max.
- Incidence of subjects with a ≥ 10 fold increase in anti-drug antibody titer and/or a ≥ 4 fold increase in anti-hIL-3 antibody titer will be tabulated.
- Complete response, objective response, and complete response rates will be tabulated with 95% clopper exact CIs for subjects with a ≥ 10 fold increase in anti-drug antibody titer and/or a ≥ 4 fold increase in anti-hIL-3 antibody titer.
- Descriptive statistics will be provided for the count of AEs, AESIs, Immune-complex related AEs, serious AEs, and AEs leading to Discontinuation by antibody status and the fold increase populations previously described.

Immunogenicity parameters will be included in by-patient data listings.

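### The SAP lets Stage 4 stand for lyophilized drug, most clearly in the immunogenicity summaries, although its own supply rule does not make the two groups the same

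*SAP*

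**What the plan says.** Three places in the SAP link Stage 4 directly with the lyophilized product. SAP 1.1 says that "Patients enrolled into Stage 4 were treated with lyophilized formulation of tagraxofusp". SAP 3.13.4 describes the lyophilized product as the one given in Stage 4. SAP 4.5 lists, among its immunogenicity groups, "Stage 4 (lyophilized formulation) only".

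SAP 1.2.1 is narrower. There the lyophilized product was "supplied for dosing in selected patients with AML in Stage 2 and for BPDCN patients enrolled in Stage 4 after 17 March 2017", and one aim of Stage 4 is "to evaluate the lyophilized formulation in a subset of patients". The protocol (synopsis and 6.2.2) likewise gives lyophilized drug to Stage 4 patients enrolled once Stage 3 enrollment was complete, and keeps anyone who started on frozen drug on that form.

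On entry to Stage 4, SAP 1.1 says "Stage 4 initiated enrollment after August 29, 2016 through January 7, 2019", and SAP 3.1 says that the 5 R/R patients "enrolled in this study after 29 August, 2016 were enrolled in Stage 4". Protocol 12.3 uses a different date: "any patient with R/R BPDCN enrolled in this study on or after 26 October, 2016, will be allocated to Stage 4". SAP 1.1 admits first-line patients to Stage 4 only after 17 March 2017.

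**The concern.** A primary objective of Stage 4 is to characterize the efficacy and safety of the lyophilized product in first-line and R/R BPDCN. If stage stands in for formulation, two errors become possible. R/R patients who entered Stage 4 before Stage 3 closed, and so would have had frozen drug, could be counted as lyophilized. Lyophilized-treated patients outside Stage 4 could be left out of the lyophilized group. Immunogenicity is where this matters most, because SAP 4.5 names its lyophilized group by stage. SAP 2.1 groups patients by planned or actual dose level and gives no rule for formulation received.

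**Working it through.** This is a question of classification, so the check is a reconciliation of counts and dates.

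**1. Stage 4 counts.** SAP 3.1 gives 39 first-line patients enrolled (37 treated, 2 screen failures) and 5 R/R patients.
- Enrolled: 39 + 5 = 44.
- Treated: 37 + 5 = 42.

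Both match the 44 enrolled and 42 treated in SAP 1.1.

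**2. Who could be in Stage 4 on frozen drug.** Stage 3 enrolled from 26 October 2016 to 17 March 2017 (SAP 3.1).
- First-line Stage 4 patients all enrolled after 17 March 2017 (SAP 1.1), so none of the 37 treated is in question.
- R/R patients could enter Stage 4 earlier. Under the supply rule in SAP 1.2.1 and protocol 6.2.2, any who did so before Stage 3 closed would have started, and stayed, on frozen drug.

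**3. Length of that window**, counted inclusively, with Stage 4 enrollment ending on 7 January 2019:
- SAP start (30 August 2016 as first day): 200 of 861 days, 200/861 = 23%.
- Protocol start (26 October 2016): 143 of 804 days, 143/804 = 18%.

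**4. How many patients.** No R/R enrollment dates are given, so the bounds are 0 and 5.
- Share of treated Stage 4: 0/42 = 0% to 5/42 = 11.9%.
- If R/R accrual had been uniform (an assumption, for scale only): 5 × 200/861 = 1.2 patients, or 5 × 143/804 = 0.9.

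The 42 is the treated count. The Immunogenicity Population in SAP 2.1 also requires sufficient samples and its size is not stated, so 11.9% is not a percentage of the SAP 4.5 group.

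**5. Evidence for the lower bound.** SAP 1.1 describes the same 44 patients as enrolled after the data cut-off for the original study report. Whether that cut-off is 25 September 2017 (SAP 3.13.3) or 9 May 2018 (the date in SAP 1.1), it falls after 17 March 2017. Read literally, all 5 R/R patients then had lyophilized drug. That reading sits uneasily with the August 2016 start of Stage 4 in the same section, and with its remark that limited Stage 4 data existed at filing. Only enrollment dates can settle it.

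**6. Lyophilized drug outside Stage 4.** SAP 1.2.1 records supply for selected Stage 2 AML patients. However many were dosed, a group restricted to Stage 4 cannot contain them. This does not depend on the R/R dates.

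**7. Lyophilized safety tables.** Protocol 12.5 calls for separate safety tabulations of lyophilized-treated patients, with no restriction by disease or line. The matching sentence in SAP 4.4 opens with first-line BPDCN patients at 12 µg/kg/day and then adds those given lyophilized drug. It can be read as a first-line subset or as a separate group.

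**The case against.** The strongest reply is that the SAP does not rely on stage alone. SAP 3.5 says summaries will be shown by stage and by formulation, and SAP 4.1 counts patients on each product, so formulation must be known for each patient. The sentence in SAP 1.1 is introductory text, not an analysis-set definition. The main frozen versus lyophilized comparison, first-line Stage 3 against Stage 4, is clean. All of this stands, and it limits the point. It does not remove it: Table 3-1 has columns by stage only, SAP 4.3 presents efficacy by stage and line, and SAP 4.5 explicitly names the group by stage.

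A reader might go further and infer that R/R patients were in fact misclassified, or that all 5 in the R/R Stage 4 efficacy column are mislabelled. The documents support neither. No R/R patient is shown to have had frozen drug. The Table 3-1 column is labelled by stage, so a Stage 4 patient belongs there whatever the product; the risk is only that the column is read as a lyophilized result. A reader might also take SAP 4.4 as clearly excluding R/R and AML patients from the lyophilized safety tables. Its wording is ambiguous and can be read consistently with protocol 12.5.

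**Conclusion.** The inconsistency is real and should be corrected, but its reach is limited. It bears on the immunogenicity group in SAP 4.5, the statements in SAP 1.1 and 3.13.4, any reading of R/R Stage 4 results as lyophilized results, and an unclear sentence in SAP 4.4. Between 0 and 5 of 42 treated Stage 4 patients (0% to 11.9%) may have had frozen drug, and an unstated number of lyophilized-treated Stage 2 AML patients would be missing from the SAP 4.5 group. The upper bound assumes that the supply rule in SAP 1.2.1 and the protocol was followed and that all 5 R/R patients enrolled before Stage 3 closed. The lower bound follows from the literal reading of SAP 1.1. The Stage 3 primary test, the 37 treated first-line Stage 4 patients and the Stage 3 versus Stage 4 similarity tests do not change.

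**What to change.** - **SAP 4.5:** replace the Stage 4 group with all patients who received lyophilized drug, assigned by product actually received.
- **SAP 4.4:** state that the lyophilized safety tabulation covers every lyophilized-treated patient (first-line, R/R and AML), in line with protocol 12.5.
- **R/R Stage 4 efficacy results:** add a footnote giving the number of patients on each formulation.
- **SAP 1.1 and 3.13.4:** reconcile with SAP 1.2.1.
- **R/R entry to Stage 4:** reconcile the SAP date (after 29 August 2016) with the protocol date (on or after 26 October 2016), and check both against the SAP 1.1 statement that all 44 patients enrolled after the original cut-off.

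The cost is SAP wording and one grouping flag. The disposition counts in SAP 4.1 already need formulation for each patient, so no new data are required.

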1.1.1. Definitions

For the purpose of this document and related analyses:

- Patients who have not received any prior treatment for their disease are considered “first-line.”
- Patients who have received any prior treatment, regardless of duration or documentation of prior response, are considered “relapsed/refractory,” abbreviated R/R.
- The frozen-liquid formulation of tagraxofusp, abbreviated “frozen”, was approved for treatment of BPDCN patients in 2019.

-
- The lyophilized formulation of tagraxofusp, abbreviated “lyo”, is considered an experimental product.

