4.2 Secondary Objectives

The secondary objectives are to:

- Determine the CR rate (i.e., CR + CRi + CRc) for Stage 1 and Stage 2, and ORR for Stage 3 patients.
- Estimate duration of response (DOR), PFS, and OS in patients with BPDCN.

- Enable preliminary characterization of the estimated ORR in patients with R/R AML, including in subsets of patients with R/R AML based on pre-treatment blast count, cytogenetics, or CD123 measurement.
- Estimate DOR, PFS, and OS in patients with AML.
- Characterize the pharmacokinetics (PK) and immunogenicity of SL-401.

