5.2 Patient Inclusion Criteria

To be included in the study, a patient must meet the following criteria:

1. The patient has a diagnosis of AML (Protocol Stages 1 and 2) or BPDCN (Protocol Stages 1-4) according to WHO classification (AML; excluding acute promyelocytic leukemia [APL, FAB M3]) or confirmed by hematopathology (BPDCN) (Facchetti et al. 2008).
2. The patient must meet one of the following (a) or (b) or (c):
 - (a) Has evidence of persistent or recurrent AML (Protocol Stages 1 and 2) in the peripheral blood and/or bone marrow that is refractory to, or has relapsed from, their most recent prior line of treatment.
 - A prior line of treatment is considered an induction regimen if it involves an approved or investigational cytotoxic chemotherapy agent, biological agent, and/or hypomethylating agent administered alone or in a combination regimen, with the intent to induce robust cytoreduction (i.e., CR).
 - The previous induction regimen may have been a SCT with intent to induce a CR.
 - Consolidation and/or maintenance (including SCT) may have been given in CR/CRi, but are not counted as a line of treatment.

- Hydroxyurea will not be considered a prior line of treatment.

(b) Has previously untreated AML (Protocol Stages 1 and 2) and is considered to be at high risk for disease progression and/or is unlikely to derive more than transient benefit from standard therapy by having at least one of the following:

- Treatment-related AML, except if it is associated with favorable cytogenetics (e.g., inversion 16, t[16;16], t[8;21], t[15;17]), and not a candidate for SCT in their current disease state.
- AML with antecedent hematological disease (e.g., MDS, myelofibrosis, polycythemia vera) and not a candidate for SCT.

(c) Has histological and/or cytological evidence of BPDCN by pathologic assessment at the investigative site according to WHO classification ([Facchetti et al. 2008](#)) by a pathologist with expertise in hematologic malignancies, that can be measured for treatment response and is either:

- Previously untreated (i.e., first-line) (Protocol Stages 2-4).
- Persistent or recurrent in the peripheral blood, bone marrow, spleen, lymph nodes, skin, or other sites after previous treatment with at least 1 line of systemic therapy for BPDCN, e.g., stem cell transplant or chemotherapy (Protocol Stages 1, 2, and 4). A pathology specimen must be available for central pathology review for all BPDCN patients enrolled in Protocol Stages 2-4.

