11. The patient has uncontrolled intercurrent illness including, but not limited to, uncontrolled infection, disseminated intravascular coagulation, or psychiatric illness/social situations that would limit compliance with study requirements.
12. The patient is pregnant or breast feeding.
13. The patient has known positive status for human immunodeficiency virus or active or chronic Hepatitis B or Hepatitis C.
14. The patient is oxygen-dependent.
15. The patient has any medical condition which in the opinion of the Investigator places the patient at an unacceptably high risk for toxicities.
16. The patient has AML and requires more than 1g per day of hydroxyurea. (Hydroxyurea is permitted at doses of 1g per day or less).

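### The SAP defines relapsed/refractory more broadly than the protocol's entry criteria and does not declare the difference

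*SAP*

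**What the plan says.** **SAP 1.1.1 (Definitions)** has two bullets on line of therapy, for this document and its analyses. On first-line: "Patients who have not received any prior treatment for their disease are considered" first-line. On R/R: "Patients who have received any prior treatment, regardless of duration or documentation of prior response, are considered" R/R. Neither bullet has a condition on systemic therapy, a rule for counting lines, or an exception for hydroxyurea.

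**Protocol 5.2, inclusion 2(c) (BPDCN)** offers two routes. One is "Previously untreated (i.e., first-line) (Protocol Stages 2-4". The other is persistent or recurrent disease "after previous treatment with at least 1 line of systemic therapy for BPDCN, e.g., stem cell transplant or chemotherapy".

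**Protocol 5.2, inclusion 2(a) and 2(b) (AML)** separates disease refractory to or relapsed from the latest line (2a) from untreated high-risk disease (2b). Under 2(a): "Hydroxyurea will not be considered a prior line of treatment". Exclusion 16 in Protocol 5.3 shows that AML patients may be taking the drug at entry: "Hydroxyurea is permitted at doses of 1g per day or less".

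**Where line is used.** Protocol 4.2 has the secondary objective "Enable preliminary characterization of the estimated ORR in patients with R/R AML", repeated in SAP 1.1.2. SAP 1.1 plans additional analyses of R/R AML and of first-line high-risk AML. SAP Table 3-1 splits BPDCN efficacy by line.

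**Declaration.** SAP 1.1.4 undertakes to set out differences from the protocol's planned analytical objectives. Neither SAP 1.1.3 nor SAP section 5 mentions the definition of R/R.

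**The concern.** Line of therapy is decided twice, at entry by the protocol and at analysis by the SAP, and the two rules differ. A patient can therefore enter under one label and be analysed under another, or enter with no valid label and still be given one.

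The gap is plausible clinically. Protocol 3.1 says about 90% of BPDCN cases begin mainly in the skin, where local treatment is conceivable. Exclusion 3 bars only wide-field radiation, and only within 14 days of entry. SAP 4.2 plans to summarise prior radiation therapy. In AML, hydroxyurea at entry is expressly allowed.

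Two things are at stake: whether the descriptive R/R AML response rate is estimated in the group the protocol calls R/R, and whether a locally treated BPDCN patient has a settled line and a settled place in the efficacy population. The R/R BPDCN groups are small: 13 patients in the Stages 1 and 2 interim analysis (SAP 3.13.1) and 5 in Stage 4 (SAP 3.1).

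**Working it through.** **1. The two rules side by side**

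| Patient | Protocol 5.2 | SAP 1.1.1 |
|---|---|---|
| BPDCN, no prior treatment | First-line | First-line |
| BPDCN, persistent or recurrent after a systemic line | R/R | R/R |
| BPDCN, local treatment only | Neither category | R/R |
| AML, refractory to or relapsed from latest line | R/R, 2(a) | R/R |
| High-risk AML, hydroxyurea only | Untreated, 2(b) | R/R |

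The rules disagree in the third and fifth rows only.

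**2. AML row.** Inclusion 2(a) needs a prior line, and hydroxyurea is not one. A hydroxyurea-only patient can therefore enter only through 2(b). If hydroxyurea counts as treatment under SAP 1.1.1, which makes no exception, the same patient becomes R/R.

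**3. Local-only BPDCN row.** This patient is not untreated and has had no systemic line, so meets neither part of 2(c). SAP 2.1 and Protocol 12.2 require mITT patients to be eligible at screening, which would exclude the patient from efficacy. The mITT definition in the protocol synopsis omits that condition. If a site had entered such a patient in Stage 3 as untreated, SAP 1.1.1 would call the patient R/R, and Table 3-1 has no R/R column for Stage 3.

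**4. Size in AML.** Let the protocol-defined R/R group have x responders among N, and add k hydroxyurea-only patients with j responders.

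Shift = (x + j)/(N + k) − x/N = [k/(N + k)] × (j/k − x/N)

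The second factor lies between −1 and 1, so the shift cannot exceed k/(N + k). N and k are not given for the final data. Assuming N = 36 (the planning figure in Protocol 12.3):
- k = 1: at most 1/37 = 2.7 points
- k = 3: at most 3/39 = 7.7 points

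**5. Size in BPDCN, as an illustration only.** Protocol 3.7.2 gives interim CR rates of 74% of 19 first-line and 31% of 13 R/R patients, all doses. These reproduce as 14/19 = 73.7% and 4/13 = 30.8%. Suppose one patient entered as first-line had to move to R/R:
- a non-responder: first-line 14/18 = 77.8%, R/R 4/14 = 28.6%
- a responder: first-line 13/18 = 72.2%, R/R 5/14 = 35.7%

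For three patients, the first-line rate would lie between 11/16 = 68.8% and 14/16 = 87.5%, and the R/R rate between 4/16 = 25.0% and 7/16 = 43.8%. In Stage 4, one patient added to the 5 R/R patients would be 1/6 = 16.7% of that group.

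**6. Stage 3.** The plan states at least 90% power with 10 patients, a 60% CR rate and a Clopper exact lower bound above 10%. With 10 patients, 3 responders give a lower bound of 6.7% and 4 give 12.2%, so 4 are needed. P(at least 4 of 10 at 60%) = 94.5%, which agrees with the plan. For 11, 12 and 13 patients the required responders are 4, 5 and 5, with power 97.1%, 94.3% and 96.8%.

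**The case against.** The strongest reply is that the definitions agree where it matters most. First-line BPDCN means untreated in both documents, and every BPDCN patient with a systemic line is R/R in both. No BPDCN patient who meets an entry category changes line. This stands.

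Second, a locally treated BPDCN patient fails eligibility, so under SAP 2.1 drops out of the efficacy analysis. A reader might infer that the broad rule improves R/R BPDCN response by mixing in lightly treated patients. The mITT definition in SAP 2.1 and Protocol 12.2 does not support that. What remains is that SAP 1.1.1 gives a line to a patient whom the eligibility rule excludes, and the synopsis wording on mITT does not settle the matter.

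Third, a reader might infer that every efficacy and safety table is affected. That is not so for AML: SAP 4.1, 4.2, 4.3.6.2 and 4.4 present AML as one group, and Table 3-1 has no AML column. The effect is confined to the R/R AML objective and the additional AML analyses in SAP 1.1, which are descriptive.

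Fourth, the SAP does not say outright that hydroxyurea is prior treatment, and SAP 4.2 already plans summaries and listings of baseline data and prior therapy. Both are fair. The first is a reason to say so explicitly; the second makes the check cheap but does not state the rule.

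**Conclusion.** The SAP's R/R definition is broader than the protocol's, the difference is undeclared, and the two should be reconciled. The consequence that follows from the wording is limited: hydroxyurea-only high-risk AML would be counted as R/R AML, and local-only BPDCN has an inconsistent line and mITT status.

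A reader might go further and conclude that patients were analysed in a line other than the one they entered under. The documents show only that this could happen; they give no count. Nor do they suggest that patients would be moved according to outcome, since line depends on history before treatment. The pivotal result is not in question: the first-line definition is common to both documents, and Stage 3 power is 94% to 97% for 10 to 13 patients.

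A reader might also take one divided by the group size as the shift per reclassified patient. That is the effect of changing one response with the denominator fixed. Removing one of the 13 interim R/R patients gives 3/12 = 25.0% or 4/12 = 33.3%, a change of −5.8 or +2.6 points, not 1/13 = 7.7 points either way.

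The AML ceilings of 2.7 and 7.7 points rest on an assumed 36 R/R patients, one or three additions, and hydroxyurea counting as treatment under the SAP.

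**What to change.** In SAP 1.1.1:
- define R/R AML by inclusion 2(a), stating that hydroxyurea does not count as a prior line;
- define R/R BPDCN by inclusion 2(c), that is, persistent or recurrent disease with one or more prior systemic lines;
- keep first-line BPDCN as previously untreated. Redefining it as having no prior line would contradict the protocol and loosen the pivotal population.

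State one classification for BPDCN patients with local treatment only, including whether they belong to mITT, and use it in both documents. It should not be assumed that they are first-line. Declare the difference from the protocol in SAP section 5, and list every patient whose entry line and analysis line differ.

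The cost is a wording change and one listing from prior-therapy data already collected (Protocol 8.2, SAP 4.2). A few patients may move columns.
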